10.1.5 Ability to eat/drink the contrast agents

Subjects will assess taste, smell, consistency, ability to swallow and fullness on a five degree-scale:

6. Very negative/Very difficult/very full
7. Negative/difficult/ full
8. Neutral/medium/medium full
9. Positive/easy/barely full
10. Very positive, good/very easy/not at all full.

Subjects will be handed an assessment form, see appendix 2, to be filled out during the period when the contrast agents are consumed.

10.1.6 CT-scan examination

The CT-examination will be started within 10 minutes after the contrast agent has been consumed and the CT-examination as a whole lasts in average eight minutes.

The CT-equipment comes with a moving table and a fixed gantry in which the X-ray tube is rotating with 2 revs per sec. The subject will be positioned in supine on the table with hands-over-head, and prone for dedicated examination of the bowels. The table is then moved into the gantry for exposure of the abdomen. Before the examinations starts, an intravenous injection of an iodine based contrast medium (Omnipaque 350 mg I/mL) is given in order to enhance any existing lesion or disease. The dose is adjusted to body weight and kidney function and is usually given in the range of 60 to 115 ml of Omnipaque 350 mg I/mL. The dose and batch number of iodine will be noted in the eCRF.

At contrast peak in the aorta, and an extra fixed delay of 50 seconds, altogether approximately one minute, exposure starts and the table moves ahead while the body part is continuously irradiated from the rotating X-ray tube. The whole procedure is finished within 10 seconds and images presented within 30 seconds.

A quality check of the CT-examination images is performed (in rare cases at the discretion of the X-ray nurse a second exposure is performed if the quality is poor) and affirmation of the subject's well-being, the subject is free to leave the CT-scanner.

10.2 Safety Parameters

10.2.1 Adverse Event

Any untoward medical occurrence in a subject or clinical trial subject administered a medicinal product and which does not necessarily have a causal relationship with this treatment.

Comment: An AE can therefore be any unfavourable and unintended sign (including an abnormal laboratory finding), symptom, or disease temporally associated with the use of an investigational medicinal product, whether or not considered related to the investigational medicinal product.

10.2.2 Adverse Reaction

All untoward and unintended responses to an investigational medicinal product related to any dose administered.

Comment: All AEs judged by either the reporting Investigator or the Sponsor as having a reasonable causal relationship to a medicinal product qualify as adverse reactions. The expression reasonable causal relationship means to convey in general that there is evidence or argument to suggest a causal relationship.

10.2.3 Unexpected Adverse Reaction

An adverse reaction, the nature or severity of which is not consistent with the applicable product information (e.g. IB for an unauthorised IP or summary of product characteristics for an authorised product).

Comment: When the outcome of the adverse reaction is not consistent with the applicable product information this adverse reaction should be considered as unexpected.

10.2.4 Serious Adverse Event

Any untoward medicinal occurrence or effect that at any dose:

- Results in death
- Is life-threatening
- Requires hospitalisation or prolongation of existing hospitalisation
- Results in persistent or significant disability or incapacity
- Is a congenital anomaly or birth defect

Comments: Life-threatening in the definition of an SAE or serious adverse reaction refers to an event in which the subject was at risk of death at the time of event; it does not refer to an event which hypothetically might have caused death if it was more severe.

Medical judgement should be exercised in deciding whether an AE/reaction is serious in other situations. Important AEs/reactions that are not immediately life-threatening or do not result in death or hospitalisation but may jeopardise the subject or may require intervention to prevent one of the other outcomes listed in the definition above, should also be considered serious.

10.3 Reporting of Adverse Events

All trial subjects will be carefully monitored for the occurrence of AEs during the trial period, from start of intake of the first dose until the contact 2, telephone interview 12 – 48 hours after the CT-examination. Reported AEs will be followed up (see 10.4 below). The Investigator will collect AEs with a non-leading question such as “have you experienced any new health problems or worsening of existing conditions” as well as reporting events directly observed or spontaneously volunteered by subjects.

Clearly related signs, symptoms and abnormal diagnostic procedure results should be grouped together and reported as a single diagnosis or syndrome whenever possible.

All AEs including but not limited to events reported by the subject, or reported in answer to an open question by the Investigator or member of this team, which fall into any of the above definitions must be recorded as an AE in the eCRF and should include the following information:

- Brief description of the event (diagnosis)
- Start date (and time, if relevant)
- Stop date (and time, if relevant) (or resolution)
- Severity
- Action taken regarding trial treatment
- Opinion on causality

- Seriousness
- Outcome

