7 OVERALL DESIGN AND PLAN OF THE TRIAL

7.1 Overview

An open, randomized, controlled, single centre phase 2 trial.

Blinding of the trial is not possible due to the clear differences in the features and properties of the contrast agents. Thus, subjects will be able to identify the contrast agent through taste and consistency and the investigators will be able to identify which contrast agent the subject has been given through its unique image grey-scale

Subjects referred for abdominal or thoracoabdominal CT-examination will be invited by letter to participate in the study. This invitation is added to the referral letter that informs them on day and time for the CT-examination. Referral letters are routinely sent out within 4 weeks prior to the examination. All subjects who has received an invitation letter will be contacted by phone by a study nurse. Those subjects who are interested in participating will be forwarded a full subject information about the trial and they will be asked to read it prior to the CT-examination visit.

Patients at the oncology departments at the hospital of Lund and Malmö will also be informed about the trial. Posters will be placed at the departments and invitation letters will be handed out to those interested.

Subjects still interested in participating in the trial will, upon arrival to the clinic at the day of CT examination, be fully informed about the trial by the investigator and given opportunity to ask questions. Eligible subjects will sign the consent to participate form prior to randomisation and any treatment related procedures.

Subject demography, medical history and concomitant medication will be recorded, and a clinical chemistry blood sample (2 mL) will be taken just prior to drinking the oral contrast agent.

Lumentin® 44 is given in volumes of 750 mL to 1 200 mL and Omnipaque® and Movprep® is given according to the general praxis of care at the department "Verksamhetsområde Bild och funktion Skånes Universitetssjukhus". At least 750 mL of Lumentin® 44 must be drunk. At least the recommended, according to the general praxis of care, volume of Omnipaque® and Movprep® must be drunk.

The subjects will be asked to drink the solutions of oral contrast agents within one hour. Subjects not able to drink at least 750 mL of Lumentin® 44 or, at least the recommended dose of Omnipaque® and Movprep®; will be classified as major protocol violators and the subject will be excluded from all efficacy evaluations.

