7.2.3 Safety Variables

The safety parameters consist of:

- Especially solicited adverse events (AEs), i.e. stomach ache, burping, letting go of wind, Nausea and sensation of fullness
- Any treatment emerging adverse events
- Any treatment emerging adverse drug reactions (ADR)
- Safety laboratory evaluations (clinical chemistry)
- The reasons for withdrawal from the trial

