13.4.5 Adverse Events

AEs will be coded using the latest available version of the MedDRA, the version of which will be provided in the clinical trial report.

Pre-treatment AEs are AEs with onset prior to the intake of the contrast agent (Visit 1) that either stop prior to first administration of trial drug or are ongoing but do not deteriorate with respect to severity and/or relationship to trial drug after start of trial treatment. Pre-treatment AEs will be listed separately and will not be included in the AE tabulations. All other AEs will be considered as treatment-emergent AEs (TEAEs) and will be summarised per treatment group for the whole trial period.

An overall summary table will be provided showing the number and percentage of subjects with any:

- AE
- TEAE
- Severe TEAE

- Serious TEAE
- AEs leading to withdrawal
- Drug-related TEAE
- Drug-related severe TEAE
- Drug-related serious TEAE
- TEAE leading to withdrawal
- TEAE with outcome death

The two-sided p-values of Fisher's exact test for the 3 comparisons "Lumentin® 44 versus diluted Omnipaque®", "Lumentin® 44 versus p Movprep®" and "diluted Omnipaque® versus Movprep®" with regard to the percentages of subjects affected will be given in the overall summary table. The number of reported AEs will also be shown in this summary table.

The above summary table may be repeated, stratified by randomisation stratification factors.

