Tack på förhand för att ni hjälper oss med att utvärdera kontrastdrycken!

Kontrastdryckens egenskaper:

	Mycket-negativ	Negativ	Neutral	Positiv	Mycket-positiv
Smak					
Lukt					
Konsistens					
	Mycket-svårt	Svårt	Medium	Lätt	Mycket-lätt
Drickbarhet					
	Mycket-mätta	Mätta	Lagom-mätta	Omätta	Mycket-omätta
Mättnadskänsla					

Ifyller av studiepersonal

Patientnummer:

Patient-Id:

Datum: År Månad Dag Studiesjuk-Signatur:

Appendix 3

Protocol: LUM-001, Version: 1.0

→

Rapporteringsformulär inför uppföljningssamtal 12-48 timmar efter CT-undersökning

Patientnummer:

Patient Id:

Vid uppföljningssamtalet följes nedan angivna beskrivning. Det är av vikt att alla patienter utfrågas på ett likvärdigt sätt för att få en så objektiv bedömning av eventuella biverkningar och användande av läkemedel.

Börja intervjun med att fråga om patienten tagit några läkemedel sedan sist eller ändrat sin dosering av redan rapporterad pågående läkemedelsbehandling. För pågående läkemedelsbehandling, var god se patientens journal.

Använd en öppen fråga, t.ex: har ni tagit något läkemedel sedan ni lämnade kliniken efter er CT-undersökning eller ändrat eller slutat ta eventuell behandling ni har haft?.

⊕

Har patienten tagit något nytt läkemedel eller ändrat pågående medicinering?

Jas	Nej
	

Om patienten har tagit nytt läkemedel eller ändrat sin medicinering fylls patientjournalens "concomitant medication form" i.

Fråga därefter ut patienten om eventuella biverkningar. Använd en öppen fråga, t.ex: har ni haft några besvär eller obehag sedan ni lämnat kliniken efter er CT-undersökning?.

Har patienten rapporterat någon biverkan?

Jas	Nej
	

Om patienten svarar ja på denna fråga så fylls patientjournalens "AE form" i. Använd en AE form för varje enskild biverkan.

..... Sidbrytning

Protocol: LUM-001, Version: 1.0 →

¶

Om patienten har rapporterat någon biverkning under tiden på kliniken och denna fortfarande var pågående när patienten lämnade kliniken, så frågas patienten ut om det skett några förändringar. ¶

¶

Har patienten rapporterat förändring på pågående biverkan? ☐

Jaa	Nej
☐	☐

Notera eventuella förändringar i patientjournalens "AE form". Använd en AE form för varje enskild biverkan. ¶

¶

¶

Därefter frågas patienten ut om han/hon haft problem med: ¶

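### The five solicited symptoms are not assessed before intake, so their treatment-emergent status rests on recalled onset and worsening cannot be verified

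*Combined protocol and SAP*

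**What the plan says.** Section 7.2.3 puts these first among the safety variables: "Especially solicited adverse events (AEs), i.e. stomach ache, burping, letting go of wind, Nausea and sensation of fullness".

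Section 10.3 sets the start of the AE window: "All trial subjects will be carefully monitored for the occurrence of AEs during the trial period, from start of intake of the first dose". The window ends at the telephone interview, 12 to 48 hours after the scan. Each AE record carries a start date; the clock time is entered only where relevant. Under 10.3.1, an event that changes in severity is reported at its worst grade.

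Section 13.4.5 sorts events by onset. It begins "Pre-treatment AEs are AEs with onset prior to the intake of the contrast agent (Visit 1"), and requires that such events either stop before the first administration or "are ongoing but do not deteriorate with respect to severity and/or relationship to trial drug after start of trial treatment". The default is stated next: "All other AEs will be considered as treatment-emergent AEs (TEAEs) and will be summarised per treatment group for the whole trial period". Fisher's exact test then compares the percentages of subjects affected for all three pairs of agents.

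The Visit 1 list (12.1.2) and both schedules (1.1 and Table 4) contain demography, concomitant medication and illness, medical history, blood samples before and after the agent, and a general AE entry. None has a pre-intake check of the five symptoms. Appendix 3, the telephone form, introduces them with "Därefter frågas patienten ut om han/hon haft problem med" (the patient is then asked whether he or she has had problems with the following). One yes/no box covers all five, and a yes leads to AE forms.

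**The concern.** The rule in 13.4.5 needs two facts for each symptom: whether it began before the drink and, if it was still present, whether it became worse. Section 10.3 opens collection only when drinking starts, so the pre-treatment category has no collection period of its own. Nothing in the visit procedures supplies a pre-intake grade.

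Pre-existing symptoms are plausible in this population. Section 7.1 says "Patients at the oncology departments at the hospital of Lund and Malmö will also be informed about the trial", and subjects arrive fasted for a clinically indicated scan. If such symptoms enter the treatment-emergent table, the absolute tolerability rate of each agent is overstated and a real difference between agents is harder to see. Tolerability is a secondary objective, and a missing baseline cannot be recovered after the visit.

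**Working it through.** **1. Which records could show the state before intake**

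| Source | What it gives | Use as a baseline |
|---|---|---|
| 10.3, AE window | Events from start of intake | None before intake |
| 10.3, AE record | Start date, optional time | Partial: onset by recall |
| 10.3.1 | One grade, the worst | No pre-intake grade |
| 11.1.2 and Visit 1 list | Diseases of the last 2 years, concomitant illness | Indirect; the five symptoms are not named |
| 10.5 | Clinically significant findings before treatment go to medical history | Placed under laboratory values; mild wind or nausea would not qualify |
| 10.1.5 and Appendix 2 | Fullness score | Given during or after drinking |
| Appendix 3 | Five symptoms, one yes/no | After intake; no item on presence before intake |

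The onset half of the rule can be applied in part, from recalled times. Intake, scan and probably most events fall on the same day, so a date without a time does not separate before from after. The worsening half has no structured data source.

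**2. Effect of misclassification**

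The plan gives no power figure for safety. Its only one, 78% in 13.6.1, concerns the primary variable and plays no part here.

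Inputs from the plan: 40 and 20 evaluable subjects (8.4), two-sided 5% level (13.2), Fisher's exact test (13.4.5). Assumed, because the documents give no rates: true treatment-emergent rates p of 50% v 10%, and a background b (the share of subjects with a pre-existing symptom counted as treatment-emergent), equal in the arms and independent of the agent's effect.

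Observed rate = 1 − (1 − p)(1 − b) = p + b(1 − p).

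Observed difference = (p1 − p2)(1 − b).

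For b = 10%: 0.50 + 0.10 × 0.50 = 0.55; 0.10 + 0.10 × 0.90 = 0.19; difference 0.36 = 0.40 × 0.90.

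Exact Fisher power by enumeration of all outcomes, 40 v 20:

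| b | Observed rates | Difference (points) | Power |
|---|---|---|---|
| 0 | 50% v 10% | 40 | 0.891 |
| 5% | 52.5% v 14.5% | 38 | 0.815 |
| 10% | 55% v 19% | 36 | 0.733 |
| 20% | 60% v 28% | 32 | 0.572 |

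With assumed true rates of 50% v 20%, power is 0.566 at b = 0, 0.430 at 10% and 0.330 at 20%.

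With equal true rates (20% v 20%), the expected difference stays 0 and the rejection probability stays at 3% to 4% for b from 0 to 30%. Misclassification dilutes a difference; it does not create one.

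**3. Partial misclassification**

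If a share m of the background is misclassified, b is replaced by m × b. If start times removed half of a 10% background, the 5% row applies: power 0.815 rather than 0.733. Each row is therefore an upper bound on the loss for a background of that size.

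**The case against.** The strongest reply is that the rule is workable. Every AE record has a start date with room for a time, and the day of intake is known. The general question in 10.3 asks for new problems or worsening of existing ones. Concomitant illness is recorded at Visit 1. Section 12.1.3 limits the telephone interview to events after the scan, and the earlier open question in Appendix 3 asks about trouble since leaving the clinic. The summary table also has drug-related rows, and causality can be graded unlikely where underlying disease is a plausible explanation. Referral for small bowel disease is an exclusion. The trial was not sized on safety.

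Much of this stands. A reader might infer that the rule in 13.4.5 cannot be applied at all; the onset field and the framing of the interview show that this goes too far. A reader might also infer that pre-existing symptoms penalise one agent, or Lumentin in particular. Randomisation makes the background equal in expectation, so the documents do not support that either. Nor do they show that misclassification will occur; it is a risk.

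What does not stand is the reply on worsening. The new-or-worse qualifier belongs to the general question, and the solicited item in Appendix 3 carries neither it nor a time window of its own. A single worst grade cannot show a change from a state that nobody recorded. The drug-related rows help only those rows, and they draw on the same recalled onset.

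**Conclusion.** The concern holds in limited form. Sections 10.3 and 13.4.5 do not fit together, and the five solicited symptoms lack a pre-intake record. Their treatment-emergent status depends on onset recalled at the telephone call, except where a subject volunteers a symptom in the clinic, and worsening cannot be verified.

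The consequence is possible inflation of absolute rates in every arm and dilution of true differences by up to (1 − b), with no expected bias between arms. The fall in power from 89% to 82%, 73% and 57% rests on assumed rates and on all of a 5%, 10% or 20% background being misclassified, so it shows direction and scale only. The primary analysis is untouched. This is an inexpensive improvement to secondary safety data, not a flaw that undermines the trial.

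**What to change.** - **Section 12.1.2 and both schedules:** at Visit 1, alongside the pre-intake blood sample and before the agent is dispensed, record presence and severity of each of the five symptoms.
- **Section 10.3:** start AE recording at consent, so that the pre-treatment category in 13.4.5 can be filled, and require an onset time for events on the day of intake.
- **Appendix 3 and 13.4.5:** count a solicited symptom as treatment-emergent only if it is new or worse than that baseline.

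The cost is about one minute per subject at a visit that already takes place, a few eCRF fields and a wording change. Asking may prompt the symptoms slightly. Because it happens before dispensing, the prompting should be equal across arms.

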12.1.2 Visit 1 (CT-scan, Day 1)

Subjects still interested in participating in the trial will, upon arrival to the clinic at the day of CT examination, be fully informed about the trial by the investigator and given opportunity to ask questions. Eligible subjects will sign the consent to participate form prior to randomisation and any treatment related procedures.

During Visit 1 the Investigator will:

- Provide the subjects with full subject information and answer any question the subject might have
- Obtain informed consent
- Check in-/exclusion criteria
- Randomise the subject
- Record demography parameters
- Record concomitant medication and illness
- Record medical history
- Take blood sample (2 mL) before and after contrast agent administration
- Dispense the contrast agent
- Record the subject's assessment of taste, smell, consistency etc.
- Check and record compliance
- Note adverse events
- Perform the CT-scan including providing iodine contrast agent
- Assess efficacy

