12.1.3 Contact 2, Telephone interview

The subject will be contacted by telephone by the investigator 12 to 48 hours after the CT-scan visit and interviewed about any possible adverse events that has occurred during the period after the CT-scan. The interview will include a set of predefined questions (see appendix XX) and also an open question, e.g. “have you experienced any untoward events or side effects since you left the clinic”. Concomitant medication and any change in concomitant medication will also be checked.

During telephone interview, the Investigator will:

- Check any occurrence or change in adverse events
- Check of use or change in concomitant medication

SAE and other AEs that the investigator assesses as relevant to follow from a trial perspective will be followed up, see section 10.4

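### The five especially solicited symptoms are asked by name as AEs only at the telephone call, so those arising during and just after intake are likely under-ascertained, and no summary of them is planned

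*Combined protocol and SAP*

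**What the plan says.** Section 7.2.3 opens its list of five safety variables with this item: "Especially solicited adverse events (AEs), i.e. stomach ache, burping, letting go of wind, Nausea and sensation of fullness". Section 6.2 makes the safety and tolerability of each of the three agents a secondary objective.

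Section 10.3 sets the AE window as running "from start of intake of the first dose until the contact 2", so the clinic visit is formally included. Its method is: "The Investigator will collect AEs with a non-leading question such as" an open enquiry about new or worsening health problems, "as well as reporting events directly observed or spontaneously volunteered by subjects". The Visit 1 procedure list in section 12.1.2 says only "Note adverse events".

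For the call, section 12.1.3 says subjects will be "interviewed about any possible adverse events that has occurred during the period after the CT-scan", and adds: "The interview will include a set of predefined questions (see appendix XX) and also an open question". The appendix number was never filled in. The matching form is evidently Appendix 3. It has an open question limited to the time since leaving the clinic ("har ni haft några besvär eller obehag sedan ni lämnat kliniken efter er CT-undersökning"), then an item on in-clinic events that were already reported and still ongoing at departure, then the five named symptoms with one yes/no answer for all of them together.

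Section 13.4.5 plans MedDRA coding, an overall table of AE categories by arm, and Fisher's exact tests for three pairwise comparisons. It has no table of the solicited symptoms and no split between solicited and unsolicited events.

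**The concern.** A symptom counts as solicited only if the subject is asked about it by name. Here that happens half a day to two days after exposure, in an interview that section 12.1.3 confines to the time after the scan. While the subject drinks about a litre, waits, is scanned and is observed, a short episode of nausea or wind enters the data only if it is volunteered, seen by staff or mentioned in reply to a general question.

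Two things are at stake. First, a named safety variable would rest on different collection methods in different periods, with the weaker method applied during exposure. Second, the events found by both methods go into the same overall AE percentages, so the report could not show how often each named symptom occurred or when. The trial is open-label and staff know the arm while deciding what to ask and record, which is a further reason to fix the questions in advance. Appendix 3 itself stresses that all patients should be questioned in the same way so that the assessment is as objective as possible.

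**Working it through.** The plan gives no figure on this point to reproduce. The check is a comparison of the texts, plus the length of the clinic window.

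**Step 1. Who is asked what, and when**

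| Period | How AEs are collected | Named-symptom AE checklist? |
|---|---|---|
| Start of intake to departure | Non-leading question, observed events, volunteered events (10.3; 12.1.2) | No |
| Same period, fullness only | Five-grade subject rating, made when going to the CT (10.1.5; Appendix 2) | No; a secondary efficacy variable (7.2.2) |
| Call, 12-48 hours after the CT | Open question, then the five symptoms (12.1.3; Appendix 3) | Yes |

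**Step 2. Length of the clinic window**

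Inputs: intake 30-60 minutes (9.2); delay to CT 0-10 minutes and CT about 8 minutes (7.1); stay of 30 minutes after the CT (synopsis, trial design).

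- Shortest: 30 + 0 + 8 + 30 = 68 minutes.
- Longest: 60 + 10 + 8 + 30 = 108 minutes.

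Section 7.1 counts the 30 minutes from the intravenous injection instead. That would remove about the 8 minutes of the CT, giving about 60-100 minutes. The conclusion does not change.

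**Step 3. Does the call reach back into that window?**

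- Section 12.1.3 limits the interview to the time after the scan. On that wording the 30-minute stay falls inside the interview's period, and the uncovered part is intake, delay and scan: 30 + 0 + 8 = 38 to 60 + 10 + 8 = 78 minutes.
- The open question in Appendix 3 starts later, at departure. On that wording the whole 68-108 minutes lies outside.
- The Appendix 3 item on in-clinic events covers only events already reported and still ongoing, so it cannot recover one that was missed.
- The lead-in to the five symptoms in Appendix 3 states no time limit. A subject might mention an in-clinic symptom from memory, but nothing tells the interviewer to ask about that period.

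The plan thus implies different starting points for the call, and none of its text directs the checklist at the intake period.

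**Step 4. Could the analysis separate the two methods afterwards?**

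Partly. Appendix 3 calls for one AE form per event, and events are MedDRA-coded. However, section 10.3 asks for onset time only if relevant and wants clearly related symptoms grouped under one diagnosis where possible. No field records whether an event was solicited, and section 13.4.5 summarises treatment-emergent AEs over the whole trial period.

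**The case against.** The strongest reply is that the clinic period is covered. AE collection starts at first intake, Visit 1 is marked for AEs in the schedule of events, staff are present, and burping at least can be observed directly. This stands against one tempting inference, that the plan misses the clinic period altogether. It does not. The supportable claim is under-ascertainment and reliance on recall.

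Second, fullness is rated by every subject in the clinic on Appendix 2 and compared between arms as a secondary variable. This also stands. The gap in structured questioning is complete only for stomach ache, burping, wind and nausea. For fullness, what is missing is its collection as an AE.

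Third, the same procedure applies in all three arms. A reader might infer that the comparison favours one agent, but the documents show no such distortion. Open-label collection makes differential questioning possible; it does not demonstrate it.

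Fourth, the documents do not show that these symptoms occur mainly in the clinic. Section 5.3 names eructation, abdominal distension and mild nausea as the commonest pilot side effects, without onset times. Onset during or soon after drinking is plausible, but it is an assumption.

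Fifth, symptom tables could be built from the coded AE forms, and section 13 allows a separate SAP to add detail. That is possible, but nothing promises it, and a table cannot restore events that were never elicited.

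**Conclusion.** The point holds as a correctable gap in ascertainment and reporting. The five symptoms are asked by name as AEs only at the call, and about 68-108 minutes in the clinic have no such checklist (38-78 minutes if the call is taken to start at the end of the scan). Four of the five symptoms are likely under-ascertained in that window, on the assumptions that some of them arise during or soon after drinking and that an open question finds fewer of them than a named one. Section 13.4.5 gives this safety variable no summary of its own.

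The loss cannot be sized from the documents. A reader might try: if 50% of subjects had a symptom in the clinic and an open question found 50-75% of what a checklist finds, then 50% x (1 - 0.75) = 12.5 to 50% x (1 - 0.50) = 25 percentage points would be missed per arm. Neither input is in the documents. The result would also be a ceiling for the tested percentage with any AE, because a subject missed in the clinic who reports any event at the call is still counted. Nor do the documents rank this variable as the main measure of tolerability; it is the first listed of five. The change is worth making before enrolment, but the primary analysis does not depend on it.

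**What to change.** - **Sections 10.3 and 12.1.2:** add the same five-item checklist, in all arms, just before the subject leaves the clinic, and keep the open question ahead of it. Record an answer for each symptom.
- **Section 12.1.3 and Appendix 3:** state the reference period of each checklist (intake to departure in the clinic; departure to call by telephone) and bring the wording about the scan and about departure into line. Replace the unfinished appendix reference, and mention the checklist in section 10.3, which now describes only the non-leading question and observed or volunteered events.
- **eCRF:** add a flag for solicited or unsolicited on each AE.
- **Section 13.4.5:** tabulate each solicited symptom by arm and period, separately from unsolicited AEs.

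The cost is about a minute per subject for staff already present, one eCRF flag and one table. The list already exists in Appendix 3, and no dose, procedure or visit changes. The downside is that more mild AEs will be recorded, so the overall AE percentages will probably rise.
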